| Procedure | Combo A During Treatment Nivo 3mg q2w + Ipi 1 mg/kg q6w | Combo B During Treatment Nivo 1 mg/kg + Ipi 3 mg/kg q3w x 4, followed by Nivo 240 mg q2w | Combo C During Treatment Nivo 240 mg + BMS-986016 80 mg q2w | Combo D During Treatment Daratumumab q1 week/q2weeks/q4 weeks + Nivo 240 mg q2 weeks/ 480 mg every 4 wks. | Notes See note sections below for dosing windows |
|--------------------------------------|--|---|---|--|--|
| Outcomes Research Assessments | | | | | |
| EORTC QLQ-C30 (Cohorts A, C, and D) | X | | X | X | Assessments to be collected at Day 1 Week 1 every 4 cycles for the first 17 cycles: Day 1 (prior to dosing) of Cycles 1, 5, 9, 13, 17; Then every 6 cycles thereafter: Day 1 (prior to dosing) of Cycles 23, 29, 35+. |
| EORTC QLQ-C30 (Cohort B) | | X | | | Assessments to be collected prior to dosing at Cycle 1 Day 1 and Cycle 4 Day 1, and then every 4 cycles for 16 cycles: Day 1 (prior to dosing) Cycles 1, 4, 8, 12, 16; Then every 6 cycles thereafter: Day 1 (prior to dosing) Cycles 22, 28, 34+ |
| EQ-5D (Cohort A, C, and D) | X | | X | X | Assessments to be collected at Day 1 Week 1 every 4 cycles for the first 17 cycles: Day 1 (prior to dosing) of Cycles 1, 5, 9, 13, 17; every 6 cycles thereafter: Day 1 (prior to dosing) of Cycles 23, 29, 35+. |

Table 5.1-3: On-Treatment Assessments Metastatic Combination Therapy Cohorts (CA209358)

| Procedure | Combo A During Treatment Nivo 3mg q2w + Ipi 1 mg/kg q6w | Combo B During Treatment Nivo 1 mg/kg + Ipi 3 mg/kg q3w x 4, followed by Nivo 240 mg q2w | Combo C During Treatment Nivo 240 mg + BMS-986016 80 mg q2w | Combo D During Treatment Daratumumab q1 week/q2weeks/q4 weeks + Nivo 240 mg q2 weeks/ 480 mg every 4 wks. | Notes See note sections below for dosing windows |
|------------------|--|---|---|--|---|
| EQ-5D (Cohort B) | | X | | | 
Assessments to be collected prior to dosing at Cycle 1 Day 1 and Cycle 4 Day 1, and then every 4 cycles for 16 cycles:
 
Day 1 (prior to dosing) Cycles 1, 4, 8, 12, 16;
 
Then every 6 cycles thereafter:
 
Day 1 (prior to dosing) Cycles 22, 28, 34+
 |

Table 5.1-3: On-Treatment Assessments Metastatic Combination Therapy Cohorts (CA209358)

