Nivolumab combined with Ipilimumab: Combo B

	Nivolumab	Ipilimumab
Dosing Schedule per Protocol	1 mg/kg every 3 weeks for 4 doses followed by 240 mg every 2 weeks	3 mg/kg every 3 weeks for 4 doses
Dose	Dose (mg) is defined as Total Dose administered (mg). Dose administered in mg at each dosing date is collected on the CRF	Dose (mg/kg) is defined as Total Dose administered (mg)/Most recent weight (kg). Dose administered in mg at each dosing date and weight are collected on the CRF
Cumulative Dose	Cum Dose (mg) is the sum of the doses administered to a subject.	Cum Dose (mg/kg) is the sum of the doses administered to a subject.
Cycle Duration _(i) (wk)	(Dose date _(i+1) - Dose date _(i))/7	N/A

Nivolumab combined with Ipilimumab: Combo B

	Nivolumab	Ipilimumab
	For the last dose N, if N<=4, cycle duration (N) (wk)=3; if N >4, cycle duration (N) (wk)=2.	
Cycle Intensity _(i) (mg/kg/wk)	Dose _(i) /Cycle Duration _(i)	N/A
Relative Cycle Intensity (i) (%)	(Cycle Intensity _(i) /intended dose per week) * 100	N/A
Relative Dose Intensity (%)	Sum of all Relative Cycle Intensities divided by N	Cum dose /[(Last dose date - Start dose date + 21) x 3/21] x 100
Duration of Treatment	Last dose date - Start dose date + 1	Last dose date - Start dose date + 1

Volume infused, volume prepared, and weight are collected on the CRF. Nominal nivolumab dose collected in IVRS. $i = 1, 2, \dots, N$, where N = number of infusions. Cycle Duration (N) = 3 weeks for nominal 1 mg/kg nivolumab doses for first 4 doses and 2 weeks for nominal 240 mg after 4th dose. Intended dose per week is xx mg (0.33 mg/kg times subject's weight in kg) for nominal 1 mg/kg nivolumab doses in the first 4 doses and 120 mg for nominal 240 mg nivolumab doses after 4th dose.

Nivolumab combined with BMS-986016: Combo C

	Nivolumab	BMS-986016
Dosing Schedule per Protocol	240 mg every 2 weeks	80 mg every 2 weeks
Dose	Dose (mg) is defined as Total Dose administered (mg). Dose administered in mg at each dosing date is collected on the CRF	Dose (mg) is defined as Total Dose administered (mg). Dose administered in mg at each dosing date is collected on the CRF
Cumulative Dose	Cum Dose (mg) is the sum of the doses administered to a subject.	Cum Dose (mg) is the sum of the doses administered to a subject.
Relative Dose Intensity (%)	Cum dose /[(Last dose date - Start dose date + 14) x 240/14] x 100	Cum dose /[(Last dose date - Start dose date + 14) x 80/14] x 100

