7.4.2 Modifications of Study Therapy

7.4.2.1 Dose Delays

Treatment may be delayed for up to a maximum of 6 weeks from the last dose. A dose will be considered as actually delayed if the delay is exceeding 3 days (i.e., greater than or equal to 4 days from scheduled dosing date) for nivolumab and ipilimumab. All studies drugs must be delayed until treatment can resume. Length of delay for study treatment is summarized in Table 7.4.2.1-1. Dose delays will be divided into following categories: 4 - < 8 days, 8 - < 15 days, 15 - < 43, ≥ 43 days. Reason for dose delay will be retrieved from CRF dosing pages.

The following parameters will be summarized by tumor type:

- Number of subjects with at least one dose delayed, number of dose delayed per subject, length of delay and reasons for dose delay

Table 7.4.2.1-1: Length of Dose Delay

Nivolumab monotherapy	
Nivolumab Dose Delay	duration of previous cycle in days - 14

Table 7.4.2.1-1: Length of Dose Delay

Nivolumab monotherapy	
Nivolumab combined with Ipilimumab: Combo A	
Nivolumab Dose Delay	duration of previous cycle in days - 14
Ipilimumab Dose Delay	duration of previous cycle in days - 42
Nivolumab combined with Ipilimumab: Combo B	
Nivolumab Dose Delay	(duration of previous cycle in days - 21) for the first 4 doses (duration of previous cycle in days - 14) starting from the 5th dose
Ipilimumab Dose Delay	(duration of previous cycle in days - 21) for the first 4 doses
Nivolumab combined with BMS-986016: Combo C	
Nivolumab Dose Delay	duration of previous cycle in days - 14
BMS-986016 Dose Delay	duration of previous cycle in days - 14
Nivolumab combined with Daratumumab: Combo D	
Nivolumab Dose Delay	(duration of previous cycle in days - 14) for the first 11 doses (duration of previous cycle in days - 28) starting from the 12th dose
Daratumumab Dose Delay	(duration of previous cycle in days - 7) for first 8 doses, (duration of previous cycle in days - 14) for 9th~16th doses, (duration of previous cycle in days - 28) after 17th doses.

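### SAP Table 7.4.2.1-1 as worded applies each new planned interval one dose too early, so an on-schedule Combo B dose 5 counts as a 7-day delay and Combo D delays are understated

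*SAP*

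**What the plan says.** SAP Section 7.4.2.1 counts a nivolumab or ipilimumab dose as delayed when it is given at least 4 days after its scheduled date. The lowest length category runs from 4 to under 8 days. Table 7.4.2.1-1 then gives the length formulas:

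- Combo B nivolumab: "duration of previous cycle in days - 21) for the first 4 doses", then "duration of previous cycle in days - 14) starting from the 5th dose".
- Combo D nivolumab: minus 14 for the first 11 doses, then "duration of previous cycle in days - 28) starting from the 12th dose".
- Combo D daratumumab: minus 7 for the first 8 doses, minus 14 for doses 9 to 16, and minus 28 after dose 17.

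The section promises the number of subjects with at least one delayed dose, delays per subject, their length and the reasons.

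SAP Section 7.4.1 (Table 7.4.1-1) gives the Combo B nivolumab schedule as "1 mg/kg every 3 weeks for 4 doses followed by 240 mg every 2 weeks". It defines the duration of cycle i as the date of dose i+1 minus the date of dose i, and adds "For the last dose N, if N<=4, cycle duration (N) (wk)=3; if N >4, cycle duration (N) (wk)=2". The table note repeats this: "Cycle Duration (N) = 3 weeks for nominal 1 mg/kg nivolumab doses for first 4 doses".

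**The concern.** The delay of a dose should be the observed gap before it minus the planned gap before it. At a change of schedule, the planned gap before the first dose of the new phase is still the old interval, because that gap was opened by the last dose of the old phase. The table attaches the new interval to that first dose. The mismatch occurs once per schedule change, at one identifiable dose.

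Where the interval shortens (Combo B, 3 weeks to 2) the formula creates delays that did not happen. Where it lengthens (Combo D, 2 weeks to 4 for nivolumab; 1 to 2 and 2 to 4 for daratumumab) it hides delays that did. At stake is the accuracy of the exposure tables. Combo B matters most, because it is the regimen being expanded in cervical cancer.

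**Working it through.** **Step 1. The planned gap from dose 4 to dose 5 in Combo B.** Doses 1 to 4 every 3 weeks fall on Days 1, 22, 43 and 64. If dose 5 falls on day D, then dose n (n at least 5) falls on D + 14(n - 5), and the week is (day - 1)/7 + 1.

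Protocol Table 5.1-3 sets Combo B questionnaires at "Day 1 (prior to dosing) Cycles 1, 4, 8, 12, 16" and then "Day 1 (prior to dosing) Cycles 22, 28, 34" onward. SAP Table 4.3-3 places the first on-treatment ones at Weeks 10, 19, 27, 35 and 47, with Week 47 at nominal Day 323.

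| Cycle | Gap 21 days (D = 85) | Gap 14 days (D = 78) | SAP Table 4.3-3 |
|---|---|---|---|
| 4 | Day 64, Week 10 | Day 64, Week 10 | Week 10 |
| 8 | Day 127, Week 19 | Day 120, Week 18 | Week 19 |
| 12 | Day 183, Week 27 | Day 176, Week 26 | Week 27 |
| 16 | Day 239, Week 35 | Day 232, Week 34 | Week 35 |
| 22 | Day 323, Week 47 | Day 316, Week 46 | Week 47, Day 323 |

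The 21-day gap reproduces all five time-points; the 14-day gap reproduces only the first. The Week 25 PK sample in Protocol Table 5.5-5 agrees. Protocol Section 5.5 says PK days are meant to fall on nivolumab days. Week 25 Day 1 is Day 169 = 85 + 6 x 14, a dosing day under the 21-day gap. Under the 14-day gap the nearest doses are on Days 162 and 176. The 3-week length of cycle 4 in SAP Section 7.4.1 says the same directly.

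**Step 2. Combo B, table applied as worded.** For a true delay of d days at dose 5, the computed delay is (21 + d) - 14 = d + 7.

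- On schedule (d = 0): 7 days, flagged, lowest category. Doses 2 to 4, and doses 6 onward, on schedule give 0.
- If the window of plus or minus 3 days in Protocol Section 4.5 applies to dose 5 (gap 18 to 24 days), the result is 4 to 10 days, so every in-window dose 5 is flagged.

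**Step 3. Combo D nivolumab.** The 240 mg doses fall at Weeks 3, 5, ..., 23, which is 11 doses; dose 12 is at Week 25, 14 days after dose 11. The computed delay at dose 12 is (14 + d) - 28 = d - 14. On schedule this is -14. It reaches the 4-day threshold only when d is at least 18, so true delays of 4 to 17 days are missed.

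**Step 4. Combo D daratumumab.** Dose 8 is at Week 8 and dose 9 at Week 9, so an on-schedule dose 9 gives 7 - 14 = -7. Dose 17 (Week 25) is due 14 days after dose 16. The minus-14 rule stops at dose 16 and the minus-28 rule starts after dose 17, so dose 17 has no rule. If the last rule was meant to include it, the result is 14 - 28 = -14.

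**Step 5. Corrected index.** Taking the planned interval from the dose that opens the previous cycle gives 0 at every on-schedule dose in all three cases.

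**The case against.** The strongest reply is that the author had the right index in mind. Table 7.4.1-1 labels cycles by the dose that opens them and uses similar breakpoints: 4 for Combo B, 11 for Combo D nivolumab, 8 and 16 for daratumumab. Read that way, the Combo B and Combo D nivolumab rows and the first daratumumab breakpoint all give zero for on-time dosing. That may well be the intent. But Table 7.4.2.1-1 describes the delay of a dose through its previous cycle, which points to the delayed dose, and a programmer who follows it literally gets the results above. The ipilimumab row does not settle the matter.

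Second, the text of Section 7.4.2.1 measures delay from the scheduled date, and on that basis an on-time dose 5 is not delayed. This is correct, but it means that text and table disagree.

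Third, the protocol never states the gap from dose 4 to dose 5 outright. Section 1.1.9 says maintenance starts at week 12. Taken as 12 elapsed weeks, that is Day 85 and agrees with 21 days. Taken as Week 12 Day 1, it is Day 78 and would make the minus 14 right, against the SAP cycle rule, the questionnaire calendar and the Week 25 sample. The window in Step 2 is also not certain to cover dose 5: Protocol Section 4.5 ties the 18-day minimum to combined dosing, and Table 5.1-3 allows 12 days between nivolumab-alone doses. These points stand and call for reconciliation.

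A reader might infer more: that nearly all Combo B subjects would be reported as delayed, that the regimen would look poorly tolerated, or that a comparison with Combo A would be distorted. The documents do not support these inferences. Exposure is summarised over all treated subjects, and the share reaching dose 5 is not given. Reasons for delay come from the CRF dosing pages, and adverse events leading to delay are analysed separately under the Core Safety SAP. Protocol Section 8.4 says randomization was not for comparison.

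**Conclusion.** The table is wrong as worded. Each Combo B subject with an on-schedule dose 5 acquires a spurious 7-day delay. The reported proportion with at least one delay therefore cannot be lower than the fraction of treated subjects whose dose 5 is on schedule. That fraction is unknown; planned Combo B numbers are about 110 cervical and 40 anogenital, the latter closed to new subjects with Revised Protocol 06.

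Combo D delays are understated by 14 days at nivolumab dose 12 and by 7 days at daratumumab dose 9. The practical weight is small: that arm is terminated, and Section 7.4.2.1 states no flagging threshold for daratumumab.

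The conclusion rests on indexing by the delayed dose and on the 21-day gap that the SAP's own calendar implies. Only descriptive dose-delay summaries are affected; ORR, DOR, PFS and OS are not.

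**What to change.** In Table 7.4.2.1-1, state that the planned interval is that of the dose opening the previous cycle, in line with Table 7.4.1-1. On the SAP's present calendar, the amount subtracted becomes:

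- Combo B nivolumab: 21 through dose 5, 14 from dose 6.
- Combo D nivolumab: 14 through dose 12, 28 from dose 13.
- Combo D daratumumab: 7 through dose 9, 14 for doses 10 to 17, 28 from dose 18. This also gives dose 17 a rule.

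Say whether the 4-day threshold is meant to cover daratumumab. Before programming, reconcile Protocol Section 1.1.9 with the SAP cycle rule and questionnaire calendar, so that the scheduled date of Combo B dose 5 is explicit. This is a request to align the documents; no dosing rule is proposed. As a check, run the program on a perfectly on-time schedule and confirm that every delay is zero.

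The cost is an index change in one SAP table and its program, plus one clarifying sentence. No new data are needed.

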7.4.2.2 Infusion Interruptions and Rate Changes

Each nivolumab, or ipilimumab infusion can be interrupted and/or the IV infusion rate can be reduced. This information will be retrieved from CRF dosing pages.

The following parameters will be summarized by cohort, tumor type and treatment:

- Number of subjects with at least one dose infusion interruption, number of infusion interruptions per subject and the reason for interruption.
- Number of subjects with at least one IV infusion rate reduction, number of IV infusion rate reduction per subject and the reason for reduction

7.4.2.3 Dose Reductions /Escalations

There will be no dose escalations or reductions of nivolumab allowed.

7.4.3 Concomitant Medications

Concomitant medications, defined as medications other than study medications which are taken at any time on-treatment (i.e., on or after the first day of study therapy and within 100 days following the last dose of study therapy), will be coded using the WHO Drug Dictionary.

The following summary tables will be provided by tumor type:

- Concomitant medications (subjects with any concomitant medication, subjects by medication class and generic term).

A by-subject listing will accompany the table.

7.5 Efficacy

Analyses from this section will be produced separately for each tumor type in different cohorts, except where otherwise indicated. In (M-3, N-3) GYN (Cervical, vaginal, and vulvar) Carcinoma, all analyses will also be conducted in two subgroups, Cervical and Vaginal/Vulvar.

7.5.1 Primary Analyses

7.5.1.1 Neoadjuvant Cohort: Rate of Surgery Delay

Rate of surgery/biopsy delay will be summarized using all treated subjects. The Clopper-Pearson method will be used to estimate the two-sided 95% confidence intervals.

Surgical summary (e.g., type of surgery, median time from last dose to surgery, reasons for surgical delay/cancellation, and any other details) will be also provided if the data are collected and available.

7.5.1.2 Metastatic Cohorts: Objective Response Rate

The ORR based on investigator assessment (Per RECIST 1.1) will be summarized. The Clopper-Pearson method will be used to estimate the two-sided 95% confidence intervals.

BOR will be summarized by response category.

To assess consistency of ORR, investigator-assessed ORR (primary analysis) will be summarized for the following subgroups by tumor type:

- Age (descriptive statistics); Age categories (< 65, ≥ 65 and < 75, ≥ 75)
- Gender (Male, Female)
- Race (White, Black, Asian, and Other)
- Region (US/Canada, Europe, Rest of the World)
- ECOG PS (0/1)
- Time from initial disease diagnosis to study entry (<= 1 year, > 1 year)
- Prior therapy (surgery, radiotherapy, and systemic cancer therapy)
- Prior lines of therapy (1, 2, 3, >=4)

- Number of prior therapy in metastatic settings (0, >=1)
- Prior platinum (yes, no) for SCCHN, GYN, cervical, anogenital HPV associated tumors
- Prior bevacizumab (yes, no) for SCCHN, GYN, cervical, anogenital HPV associated tumors
- Time from completion of most recent prior regimen to study entry (<= 3, <3 - <=6, <6 - <=9, <9 - <=12, >12 months)
- All lesions (Investigator tumor assessments at Baseline): sites of diseases, number of disease sites per subject
- Target Lesions (Investigator tumor assessments at Baseline): presence of target lesions, site of target lesion, sum of diameters of target lesions.
- Virus status (Positive / Negative) in tumor types **(M-3)** GYN (cervical, vaginal, and vulva) Carcinoma, **(MC-2a, MC-2b, MC-exp)** Cervical Carcinoma, **(MC-3a, MC-3b)** Anogenital HPV associated tumors (vaginal/vulvar/anal canal/penile), **(M-4, MC-4a)** Merkel Cell Carcinoma and **(M-5,MC-5a)** Nasopharyngeal Carcinoma (NPC), for which the virus status are tested retrospectively.

7.5.2 Secondary Analyses (Metastatic Cohorts Only)

7.5.2.1 Duration of Response Based on Investigator Assessment

DOR will be summarized for subjects who achieve confirmed PR or CR using the Kaplan-Meier product-limit method. Median values of DOR, along with two-sided 95% CI using the log-log transformation will also be calculated by cohort. In addition, the percentage of responders still in response at different time points (3, 6, and 12 months) will be presented based on the KM plot.

7.5.2.2 Clinical Benefit Rate Based on Investigator Assessment

CBR based on investigator assessment (Per RECIST 1.1) will be summarized by binomial response rates and their corresponding two-sided 95% exact CIs using Clopper-Pearson method.

7.5.2.3 Overall Survival

OS curves for each tumor type will be estimated using the Kaplan-Meier (KM) product limit method. Median OS and the corresponding two-sided 95% confidence intervals using the log-log transformation will be computed. Survival rates at 3, 6, 12, 18, 24, 36, 48, and 60 months will be estimated using KM estimates on the OS curve for each tumor type. Minimum follow-up must be longer than the time point to generate the rate. Associated two-sided 95% CIs will be calculated.

7.5.2.4 Progression Free Survival

PFS curves for each tumor type will be estimated using the Kaplan-Meier (KM) product limit method. Median PFS and the corresponding two-sided 95% confidence intervals using the log-log transformation will be computed. Survival rates at 3, 6, 9, 12 months will be estimated using KM estimates on the PFS curve for each tumor type. Minimum follow-up must be longer than the time point to generate the rate. Associated two-sided 95% CIs will be calculated.

The source of progression (death vs. progression) will be summarized.

The status of subjects who are censored in the PFS Kaplan-Meier analysis will be tabulated using following categories:

- Still on-treatment
- Received subsequent anti-cancer therapy (stem cell transplant, other)
- Progression-free in follow-up
- Off-study (lost to follow-up, withdrew consent, other).

7.5.3 Exploratory Analyses

7.5.3.1 Neoadjuvant Cohort only

- The percent change from baseline of immune cells and the percent change from baseline of select immune activation/inhibitory molecules of viral-specific T cells in tumor specific subsets of treated subjects will be evaluated. Change from baseline will be summarized using descriptive statistics (n, mean, standard deviation, median, first and third quartiles, minimum, maximum).
- The following analyses will be conducted for RFS in primary analysis and sensitivity analysis. RFS curves for each tumor type will be estimated using the Kaplan-Meier (KM) product limit method. Median RFS and the corresponding two-sided 95% confidence intervals using the log-log transformation will be computed. Survival rates at 3, 6, 9, 12 months will be estimated using KM estimates on the RFS curve for each tumor type. Minimum follow-up must be longer than the time point to generate the rate. Associated two-sided 95% CIs will be calculated. Primary RFS analysis should use censoring scheme listed in [Table 4.3-1](#). Sensitivity RFS analysis should use censoring scheme listed in [Table 4.3.1-2](#).
- The percent change in tumor volume from baseline after two doses of neoadjuvant nivolumab will be summarized using descriptive statistics (n, mean, standard deviation, median, first and third quartiles, minimum, maximum).
- Pathological complete response (pCR) rate will be summarized using all treated subjects who received surgery by a binomial response rate. The Clopper-Pearson method will be used to estimate the two-sided 95% confidence intervals. Summary of continuous % residual viable tumor (%RVT) results will be provided descriptively if the data is available.

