^a Dosing calculations should be based on the body weight assessed at baseline. It is not necessary to re-calculate subsequent doses if the participant weight is within 10% of the weight used to calculate the previous dose. All doses should be rounded up or to the nearest milligram per institutional standard.

Table 5.1-6: Follow-Up Assessments - All Subjects (CA209358)

| Procedure | X, Follow-Up ^a Visits X01 and X02 | Follow-Up Assessments for Neoadjuvant Cohort Subjects 4, 8, and 12 Months Post-Surgery ^b | S, Survival Follow-Up ^c Visits | Notes |
|---|--|--|---|--|
| Safety Assessments | | | | |
| Targeted Physical Examination | X | | | 
Lymph node areas (eg, submandibular, cervical, supraclavicular, axillary, or inguinal lymph node), and abdominal organs (eg, spleen, liver).
 
To assess for potential late emergent study drug related issues
 |
| Adverse Events Assessment | X | | X | NSAEs and SAEs must be collected up to 100 days after study drug discontinuation. SAEs that relate to any later protocol specified procedure must be collected. |
| Review of Medical History and Subsequent Cancer Therapy Information | X | X | X | |
| Laboratory Tests | X | | | CBC with differential and platelet count, BUN or serum urea level, serum creatinine, sodium, potassium, calcium, magnesium, phosphorus, chloride, bicarbonate or total CO ₂ (if locally available), amylase, lipase, glucose, AST, ALT, total bilirubin, alkaline phosphatase, LDH, albumin.. |
| Thyroid Function Testing | X | | | TSH (reflex to free T3 and free T4 if abnormal result) |
| Pregnancy Test | X | | | Serum or urine |

Table 5.1-6: Follow-Up Assessments - All Subjects (CA209358)

| Procedure | X, Follow-Up ^a Visits X01 and X02 | Follow-Up Assessments for Neoadjuvant Cohort Subjects 4, 8, and 12 Months Post- Surgery ^b | S, Survival Follow-Up ^c Visits | Notes |
|---|--|--|--|---|
| Efficacy Assessments | | | | |
| Radiographic Tumor Assessment | See Note | X | See note | Only for subjects without progression and no longer on study therapy |
| Spiral CT/MRI | | | | See Table 5.4.1-1 for Spiral CT/MRI. For subjects in the neoadjuvant cohort, radiographic tumor assessment should be at 4 mo, 8 mo and 12 mo post-surgery. ^b Subjects with a history of brain metastasis may have surveillance MRI approximately every 12 weeks or sooner if clinically indicated |
| Outcomes Research Assessments | | | | |
| EORTC QLQ-C30 | X | | | |

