| Time On Study | Assessment Frequency | Assessment Window |
|---------------|--|--|
| Screening | At screening (within 35 days of first dose) | Within 35 days of first dose |
| Pre-Surgery | Day 29 (within 7 days prior to the planned surgery date) | within 7 days prior to the planned surgery date |
| Post-Surgery | Months 4, 8, and 12 ^a | Months 4 (within ±3 weeks), 8, and 12 ^b |

^a Any images obtained prior to Month 4 as standard of care should also be assessed.

^b 4-Month Post-Surgery Assessments for Neoadjuvant Cohort Subjects may occur ± 3 weeks from scheduled time point. Follow-up assessments 8 and 12 Months Post-Surgery may occur ± 7 days from the scheduled time point. Neoadjuvant Cohort E02 and E03 Follow Up may occur at same time.

For the Metastatic Cohorts (monotherapy and combination therapy), baseline tumor assessments should be performed within 35 days prior to the first dose. Subjects will then be evaluated for tumor response beginning 8 weeks from the date of first dose (± 1 wk.), then every 8 weeks (± 1 wk.) thereafter up to 48 weeks, then it will be every 12 weeks (± 2 weeks) until disease progression is documented, or when treatment is discontinued (whichever occurs later).

For the Neoadjuvant Cohort, a Day 29 tumor scan is required for within 7 days prior to the planned surgery date.

For Neoadjuvant Cohort subjects who progress to unresectable recurrent or metastatic disease within 1 year of surgical resection or chemotherapy/radiation and receive nivolumab, a baseline tumor scan documenting progression is required prior to restarting nivolumab. Subjects will then be evaluated for tumor response beginning 8 weeks from the date of first dose of treatment (± 1 wk.), then every 8 weeks (± 1 wk.) thereafter up to 48 weeks, then it will be every 12 weeks (± 2 week) until disease progression is documented, or when treatment is discontinued, (whichever occurs later).

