4.3 Exploratory Endpoints

4.3.1 Neoadjuvant Cohort only

- The percent change from baseline of immune cells and the percent change from baseline of select immune activation/inhibitory molecules of viral-specific T cells in tumor specific subsets of nivolumab treated subjects will be evaluated. The percent change is the ratio of change from the baseline and baseline measurement.
- Recurrence-free survival (RFS), which is defined as the time from surgery to the date or recurrence (local, regional, metastasis, locally advanced unresectable recurrence, clinical or radiographic progression occurs after surgery) as determined by investigators, or death due to any cause, whichever occurs first. (Note: a subject who dies without reported recurrence will be considered to have recurred on the date of death.)

Table 4.3-1: Censoring scheme used in primary definition of RFS

Situation	Date of Recurrence or Censoring	Outcome
Recurrence (local, regional, metastasis, locally advanced unresectable recurrence, clinical/radiographic progression occurs after surgery)	Date of the earliest documented recurrence/progression after surgery	Event
Death without documented recurrence after surgery/biopsy	Date of death	Event
No post-surgery disease assessment and no death	Date of surgery	Censored
No recurrence and no death	Date of last evaluable disease assessment	Censored
New anticancer therapy ^a started without recurrence or death	Date of last evaluable disease assessment prior to or on the same date of initiation of subsequent therapy	Censored

^a Protocol allowed adjuvant therapy in SOC follow up phase is not counted as subsequent therapy.

Table 4.3.1-2: Censoring scheme used in sensitivity analysis of RFS

Recurrence (local, regional, metastasis, locally advanced unresectable recurrence, clinical/radiographic progression occurs after surgery)	Date of the earliest documented recurrence/progression after surgery	Event
Death without documented recurrence after surgery/biopsy	Date of death	Event
No post-surgery disease assessment and no death	Date of surgery	Censored
No recurrence and no death	Last known alive date	Censored
New anticancer therapy ^a started without recurrence or death	Date of last evaluable disease assessment prior to or on the same date of initiation of subsequent therapy	Censored

^a Protocol allowed adjuvant therapy in SOC follow up phase is not counted as subsequent therapy.

- Safety endpoints ([Section 7.6](#))

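### The planned 3-month RFS rate precedes any scheduled post-surgery scan, and the 12-month rate cuts the last scan window in half (minor)

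*SAP*

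**What the plan says.** RFS is an exploratory endpoint of the neoadjuvant cohort and runs from surgery: "Recurrence-free survival (RFS), which is defined as the time from surgery to the date or recurrence" (SAP 4.3.1). Clinical progression and death count as events alongside radiographic findings. In the primary censoring scheme (SAP Table 4.3-1), a subject with neither recurrence nor death is censored at "Date of last evaluable disease assessment". The sensitivity scheme (Table 4.3.1-2) uses the last date known alive instead.

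SAP 7.5.3.1 plans a Kaplan-Meier (KM) curve, a median and fixed-time rates: "Survival rates at 3, 6, 9, 12 months will be estimated using KM estimates on the RFS curve for each tumor type". It adds: "Minimum follow-up must be longer than the time point to generate the rate".

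The imaging schedule is in the protocol. Table 5.4.1-2 sets post-surgery scans at "Months 4, 8, and 12", and Table 5.1-6 agrees: "For subjects in the neoadjuvant cohort, radiographic tumor assessment should be at 4 mo, 8 mo and 12 mo post-surgery". On windows, "4-Month Post-Surgery Assessments for Neoadjuvant Cohort Subjects may occur ± 3 weeks from scheduled time point"; the Month 8 and Month 12 scans have ± 7 days. Standard-of-care images taken before Month 4 must also be assessed, but none is scheduled. No neoadjuvant scan is scheduled after Month 12.

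**The concern.** The 3/6/9/12-month list is the one used for metastatic PFS in SAP 7.5.2.4, where scans start at Week 8 and repeat every 8 weeks through Week 48. The neoadjuvant schedule is different. Neither document aligns the RFS time points with it or describes a method for recurrences known only to lie between two scans.

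Two of the four time points fit badly. At 3 months no scheduled scan has taken place, so a recurrence visible only on imaging cannot yet have been recorded unless an unscheduled image found it. At 12 months the time point falls inside the last scan window, so the accident of scan date decides whether a recurrence counts and whether a recurrence-free subject is still at risk.

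The stake is how the report reads. Revised Protocol 07 replaced PFS with RFS because it was judged the better reflection of neoadjuvant efficacy. These rates will be reported with 95% intervals for an uncontrolled cohort, and the error is in the favourable direction.

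**Working it through.** The plan gives no RFS rate or precision figure to reproduce, so the check starts from the dates.

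**Inputs from the documents.** Time points 3, 6, 9 and 12 months from surgery (SAP 7.5.3.1, 4.3.1); scans at Months 4 ± 21 days, 8 ± 7 days and 12 ± 7 days (Protocol Table 5.4.1-2); 30.4375 days per month (SAP 8); 21 evaluable subjects per tumor type (SAP 5).

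**Assumptions, not in the documents.** True 12-month RFS of 50% or 70%; exponential recurrence; scan dates uniform within their windows; a share c of recurrences found clinically at onset, the rest only by protocol scan.

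**Step 1, dates.**
- 3 months: 3 × 30.4375 = day 91.3. Month 4 window opens: 4 × 30.4375 − 21 = day 100.75. Gap: 9.4 days.
- With 30-day months the gap is 9 days; with 28-day months, 7. Only a mixed reading closes it: Month 4 as Week 16 (112 − 21 = day 91) against 3 months at day 91.3.
- 12 months: 12 × 30.4375 = day 365.25. Month 12 window: days 358.25 to 372.25, with midpoint 365.25.
- 6 months (day 182.6) and 9 months (day 273.9) fall after the Month 4 and Month 8 windows close (days 142.75 and 250.5), so they split no window.

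**Step 2, the 3-month rate.** Only clinically found recurrences are on record by day 91.3, so the expected overstatement is (1 − c) × (1 − S(3)), with S(3) = S(12)^(3/12).
- S(12) = 0.70: 1 − S(3) = 0.085. Overstatement 8.5 points (c = 0), 4.3 (c = 0.5), 1.7 (c = 0.8).
- S(12) = 0.50: 1 − S(3) = 0.159. Overstatement 15.9, 8.0 and 3.2 points.

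**Step 3, the risk set at 12 months** (n = 21, S(12) = 0.70, scan-only detection). Recurrence-free: 21 × 0.70 = 14.7. Under primary censoring about half, 7.35, are scanned after day 365.25 and are still at risk. Add recurrences after Month 8 awaiting a late scan: 21 × (0.788 − 0.70)/2 = 0.9, where 0.788 = 0.70^(8/12). Total at risk: about 8.

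**Step 4, simulated mean KM rates** (n = 21, 4,000 runs per case), in %, at 3/6/9/12 months:

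| True 12-month RFS | Found clinically | True curve | Primary analysis | Sensitivity, 12 months |
|---|---|---|---|---|
| 70% | 0% | 91.5/83.7/76.5/70.0 | 100/88.8/78.9/73.2 | 74.5 |
| 70% | 50% | same | 95.7/86.2/77.7/71.6 | 72.2 |
| 50% | 0% | 84.1/70.7/59.5/50.0 | 100/79.2/62.8/54.4 | 56.6 |
| 50% | 50% | same | 92.0/75.0/61.3/52.4 | 53.4 |

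The primary 12-month overstatement here is 1.6 to 4.4 points; repeat runs stay within about 1 to 5. Sensitivity censoring keeps subjects at risk but still omits recurrences dated in the later half of the window, so its overstatement is larger (2.2 to 6.6 points).

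**Step 5, alternatives** (70% case).
- Reading the primary KM just after the window closes (day 372.3) gives 52.9% (scan only) or 60.7% (half clinical), because scan-negative subjects are censored at their own scans and the risk set empties. A later time point is not a repair.
- Rates at 4/8/12 months with scan results set to the nominal visit give 88.9/79.0/70.0% (scan only) and 88.7/78.8/70.2% (half clinical), against true 88.8/78.8/70.0%.

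**The case against.** The best reply is that RFS is not detected by scans alone. Deaths and clinical progression count, and standard-of-care images before Month 4 are assessed. Table 5.1-6 also gives neoadjuvant subjects a targeted physical examination, including lymph node areas, 35 days after the last dose and again 80 days later. With the last dose on Day 15 and surgery on Day 29, these fall about 21 and 101 days after surgery, so the first precedes 3 months. All of this stands. It reduces the size of the problem, and Step 2 shows by how much. A reader might infer that the 3-month rate is bound to be 100%; the documents do not support that.

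Three other stronger readings also fail.
- *All four rates are wrong because each precedes its scan.* The 6- and 9-month rates carry forward the Month 4 and Month 8 scans. They sit above the assumed true curve, but that is ordinary for any KM estimate with periodic assessment, metastatic PFS included. The 12-month point lies inside its window, not before it.
- *The minimum-follow-up rule cannot be met at 12 months.* SAP 7.5.2.3 uses the same sentence for OS, where scans play no part. It most naturally means time on study, not a scan requirement.
- *The 12-month result rests on half of the recurrence-free subjects.* That describes the primary risk set on day 365.25 only. Those censored days earlier contribute to every earlier KM step, and sensitivity censoring restores them if survival follow-up shows them alive past 12 months.

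Sampling error is also large: at 70% with 21 subjects the standard error is about √(0.7 × 0.3/21) = 10 points. But the bias has a known direction, and the interval around the estimate does not reveal it.

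**Conclusion.** The mismatch is real on the documents' own figures. The 3-month rate precedes every scheduled post-surgery scan and tends to be overstated: by about 8 to 16 points with scan-only detection, 4 to 8 with half of recurrences found clinically, and 2 to 3 with 80%. The 12-month point bisects the last scan window. That omits recurrences found in the later half (about 1 to 5 points in the primary analysis) and censors recurrence-free subjects scanned in the earlier half just before the time point. The sensitivity censoring eases the second effect but not the first.

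The dates are firm. The sizes depend on the assumed RFS level, recurrence pattern, scan timing and share found clinically, none of which the documents supply.

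Severity is minor. A reader might infer that a conclusion of the trial is at risk. It is not: RFS is exploratory in a non-comparative study, with no hypothesis, threshold or decision attached, so only the interpretation of the reported rates is affected.

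**What to change.** In SAP 7.5.3.1, replace the 3/6/9/12-month RFS rates with rates at Months 4, 8 and 12. For these rates only:
- assign recurrences and censoring that arise at an in-window protocol scan to the nominal visit, with events before censoring at ties;
- keep events found clinically, on unscheduled images or at out-of-window scans at their actual dates.

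Keep the KM curve and median on actual dates under Table 4.3-1 as planned. If a 3-month rate is still shown, label it as preceding any scheduled scan.

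The cost is SAP wording and a small programming change, with no new visits or subjects. The reported early rates will be less favourable.
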